## 5.3. Secondary Aim to Evaluate Treatment Combinations

A secondary aim of the study is to evaluate treatment-order combinations after participants are allowed to cross over into other study arms. At the 3-month assessment, non-responders to randomized treatment can choose to initiate an additional treatment. This is a pragmatic approach reflecting the reality that patients in clinical care who are not happy with their initial FI treatment may choose to try another treatment. Table 7 shows the number of 3-month non-responders in each randomization group who are expected to be followed to 6, 12 and 24 months with the assumption of 15% attrition (loss to follow up or missing outcomes for other reasons) between the 3- and 12-month assessments and an additional 15% attrition between the 12- and 24-month assessments. Since non-responders can choose to try the other study treatment or SNS after 3 months, we estimate that between 5 and 50 participants will be in each of the possible treatment-order combinations at 6, 12 and 24 months. We will estimate 95% confidence intervals for the number of responders in each treatment-order combinations at 6, 12 and 24 months. We will estimate 95% confidence intervals for the number of responders in each treatment-order combinations at 6, 12 and 24 months. We will estimate 95% confidence intervals for the number of responders in each treatment-order combinations at 6, 12 and 24 months. We will estimate 95% confidence intervals for the number of responders in each treatment-order combination at each time point. Table 8 shows 95% confidence intervals for a range of group sizes and responder percentages; confidence intervals are estimated using a Wilson Score interval recommended for small sample sizes.

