#### 5.4 Estimated patient flow for this study

Figure 3 shows the estimated flow of patients through this study and identifies our assumptions regarding attrition. We estimate we will need to screen 855 patients because 2/3 will be ineligible or unwilling to be randomized. This leaves 285 to be recruited into the EMM protocol. Based on the Heymen study, we assume

15% attrition during this treatment phase and also assume that 20% (n=57) will be responders to EMM and therefore not eligible for randomization. This will leave 194 to be randomized (97 per group).

Figure 3 shows that we expect 78 from the BIO group to complete the 3-month assessment after allowing for attrition of 20% and we expect 92 from the INJ group to complete the 3-month assessment. (We assume attrition will be no greater than 5% for the INJ group because this is a low-burden treatment and also because patients will want to be screened for AEs related to INJ.) However, the statistical analysis will be by intent to treat (ITT) and will include all 194 randomized to treatment; patients who are lost to follow up prior to 3 months will be considered treatment failures. The number of patients we expect to be responders to each of the treatments at the 3-month assessment is based on the pivotal trials shown in Table 1. We separated them in this way in Figure 3 to be able to estimate the numbers of non-responders who are likely to choose an additional treatment option after 3 months. The expected number of non-responders eligible for an additional therapy at 3 months is 63 for the INJ arm^16 and 17 for the biofeedback arm^15. Assuming equal probability of choosing either of the 2 available options as an added or alternative treatment, we could expect 40 patients to choose the SNS treatment, 32 to choose BIO, and 9 to choose INJ. For the primary analyses of follow up at 6, 12 and 24 months, these non-responders will be retained in the ITT analysis as non-responders to their primary assignment at randomization. However, when we perform exploratory analyses of treatment combinations, these subjects will be treated as distinct groups and compared to patients who received monotherapy for the duration of the study. These comparisons (Aim D) are exploratory because there is insufficient power to test for significance. The left column of boxes in Figure 3 shows how we intend to follow up the responders to EMM.

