## 8.0 Statistical Considerations

## 8.1 Analysis of Primary Endpoints

Assessment of Randomized Treatment Response at 3 Months (Primary Efficacy Analysis). To test the efficacy of randomized treatment assignment, a generalized linear model with a logit link will be constructed to predict treatment response at 3 months post-randomization. Treatment group and the stratification factors of clinical site and sex will be included in the model as categorical independent variables. An ITT approach will be used in which participants will be analyzed based on their assigned treatment group regardless of actual treatment received. Participants without a valid bowel diary at 3 months due to drop out or other reasons will be classified as non-responders. Using this model, we will test the null hypothesis that the proportion of responders is the same in the two treatment groups at 3 months following randomization using an alpha of 0.05. Sensitivity analyses will be conducted to assess the impact of classifying participants with missing data as non-responders.

Assessment of Safety. The primary safety outcome is the percentage of participants in each randomized treatment group who experience an adverse event (AE) of pelvic pain of grade II or greater severity, treatment site infection, or a serious adverse event (SAE) requiring hospitalization between randomization and the 3 month assessment. Because the proportion of participants with one of these events is expected to be small, Fisher's exact tests will be used to compare the percentage of participants with a qualifying adverse event. The difference between the two treatment groups will be evaluated for significance using an alpha of 0.05. Participants who are missing safety data due to drop out or other reasons will be excluded from this analysis.

*Cost of Care Analysis.* Mean and median costs per participant will be estimated for each of the two treatment groups and from the perspectives of payers, patients, and society. We will analyze whether differences in costs through 3-month follow up across the intervention arms and perspectives are statistically significant using parametric t-tests or using non-parametric bootstrapping methods. We will evaluate differences between the two treatment groups using an alpha of <0.05.

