#### 8.2 Analysis of Secondary Efficacy Endpoints

Assessment of Efficacy through 24 months. Treatment response (≥75% reduction in weekly FI episodes) at time points through 24 months will be analyzed using a longitudinal extension of the model used for the primary efficacy analysis. Month of assessment, and interaction between month and other predictors, will be included in the model, and the correlation between measures assessed on the same participant over time will be modeled using an appropriate covariance structure. Participants classified as non-responders at 3 months will continue to be considered non-responders at subsequent time points. Participants with missing responses will be classified as non-responders, but sensitivity analyses will be conducted to assess the impact of this assumption.

Assessment of Safety through 24 months. The percentage of participants reporting AEs of pelvic pain of grade II or greater severity, treatment site infection, or an SAE requiring hospitalization by 6, 12, 18, and 24 months will be estimated with 95% confidence intervals using the Wilson Score interval method. Separate estimates will be produced for the groups of participants treated with each of the two therapies alone, and for participants in each of the treatment-order combinations. Confidence intervals will be compared descriptively.

Assessment of Cost of Care through 24 months. The median costs per participant from the perspectives of payers, patients, and society through 24 months will be estimated for each of the treatment groups, including the treatment combinations, using methods described for the primary cost of care endpoint. No formal hypothesis testing will be done, and p-values will be presented for informational purposes only.

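### Section 8.2 sets no denominator or censoring rule for 24-month safety and cost, so with the planned attrition the estimates depend on a choice not yet made

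*Combined protocol and SAP*

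**What the plan says.** For safety, Section 8.2 counts grade II or worse pelvic pain, infection at the treatment site, and any SAE that leads to hospital admission. The share of participants with such an event "by 6, 12, 18, and 24 months will be estimated with 95% confidence intervals using the Wilson Score interval method". The estimates are not by randomized arm: "Separate estimates will be produced for the groups of participants treated with each of the two therapies alone", and further ones for each treatment-order combination. They are compared descriptively.

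For cost, Section 8.2 says "The median costs per participant from the perspectives of payers, patients, and society through 24 months will be estimated for each of the treatment groups", combinations included, "using methods described for the primary cost of care endpoint". Section 8.1 describes those methods as "using parametric t-tests or using non-parametric bootstrapping methods". P-values are for information only.

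The one written rule for missing safety data is in Section 8.1 and concerns the 3-month analysis: "Participants who are missing safety data due to drop out or other reasons will be excluded from this analysis". Section 3.0, item 6, refers to statistical models for longitudinal safety and cost through 24 months, but Section 8.2 specifies no such model for either.

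On attrition, Section 5.4 says "we expect 78 from the BIO group to complete the 3-month assessment after allowing for attrition of 20" percent, and assumes at most 5% for INJ (92 of 97). Section 5.3 assumes "15% attrition (loss to follow up or missing outcomes for other reasons) between the 3- and 12-month assessments and an additional 15% attrition" over the second year. It states those two rates for 3-month non-responders.

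**The concern.** A Wilson interval is for a binomial proportion in which each person's outcome at the time point is known. Neither a t-test nor an ordinary bootstrap of cost totals deals with totals cut short by dropout. When a large share of participants leave before 24 months, someone must decide whether they stay in the denominator, whether their events count, and what cost they carry after leaving. The plan leaves this open for safety and cost, although it is explicit elsewhere in Section 8.2: missing efficacy responses are non-responses with sensitivity analyses, and the FI severity and quality-of-life scales are assumed missing at random with sensitivity analyses.

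The grouping adds to the problem. A participant reaches a combination group only by staying to the 3-month assessment, whereas the therapy-alone groups hold everyone lost before it. Follow-up also stays anchored to the first treatment (Section 3.1), so time observed on an added treatment is shorter than the time-point label suggests. Part of any descriptive difference could then be follow-up time rather than treatment. These analyses are the long-term follow-up of research objectives 2 and 3 in Section 1.1.

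**Working it through.** **1. The plan's own numbers (Sections 5.3 and 5.4, Table 7).** 97 × 0.80 = 77.6 (plan: 78) and 97 × 0.95 = 92.2 (plan: 92). Non-responders at 12 and 24 months: 17 × 0.85 = 14.5 and 17 × 0.85² = 12.3 (plan: 15 and 13); 63 × 0.85 = 53.6 and 63 × 0.85² = 45.5 (plan: 53 and 45). All agree within one participant.

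**2. Loss by randomized arm**, extending the 15% and 15% to everyone:
- BIO: 1 − 0.80 × 0.85 × 0.85 = 42.2% (about 56 of 97 followed).
- INJ: 1 − 0.95 × 0.85 × 0.85 = 31.4% (about 67 of 97 followed).

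The gap between arms arises wholly in the first 3 months. After that each arm loses 1 − 0.85² = 27.75%.

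**3. Loss in the groups compared**, assuming every 3-month non-responder adds a treatment:
- BIO alone: 19 early losses + 61 responders = 80. Followed to 24 months: 61 × 0.7225 = 44.1. Loss 45%.
- INJ alone: 5 + 29 = 34. Followed: 29 × 0.7225 = 21.0. Loss 38%.
- Combinations (Table 7): 1 − 13/17 = 24% after BIO; 1 − 45/63 = 29% after INJ.

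Early losses make up 19/80 = 24% of BIO alone, 5/34 = 15% of INJ alone, and none of the combination groups.

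**4. Effect of the denominator on safety.** Assume a true 24-month risk of 10% in both arms, constant hazard λ = −ln(0.9)/24 per month, dropout independent of events, and retention S(t) falling exponentially within 0-3, 3-12 and 12-24 months at the rates in step 2. The observed event fraction is E = ∫ λ e^(−λt) S(t) dt over 0-24 months.

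| Denominator | Formula | BIO | INJ |
|---|---|---|---|
| All participants | E | 7.1% | 8.3% |
| 24-month completers only, dropouts' data discarded | true risk | 10.0% | 10.0% |
| Event seen or followed to 24 months | E / [E + S(24) × 0.9] | 11.9% | 11.8% |

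For BIO the last row is 0.0706 / (0.0706 + 0.578 × 0.9) = 0.119.

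**5. The same check on the plan's expectations.** Section 5.2.2 expects 9.8% in INJ and 0% in BIO by 3 months. If the 9.8% all falls in month 1, the all-participant INJ figure is 9.7%, almost unbiased; the event-or-completer figure is 13.6%. With no BIO events, every denominator gives zero.

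**6. Cost, if cost after dropout is set to zero.** From Section 5.2.3, monthly FI cost is 0.75 × 2,562/12 + 1,549/12 = $289.21 for BIO and 0.50 × 2,562/12 + 0.75 × 1,549/12 = $203.56 for INJ. Adding three months to the Table 5 treatment costs gives $1,664 and $10,974, matching Table 6 ($1,664 and $10,973) within a dollar. Mean observed time, the area under S(t), is 16.9 months (BIO) and 19.8 months (INJ). Carrying the same monthly costs to 24 months, with treatment cost counted in full:
- BIO: full 796 + 24 × 289.21 = $7,737; observed 796 + 16.87 × 289.21 ≈ $5,674; 73%.
- INJ: full 10,363 + 24 × 203.56 ≈ $15,249; observed 10,363 + 19.76 × 203.56 ≈ $14,385; 94%.

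The INJ minus BIO difference goes from $7,512 to $8,711, about 16% more. These are means by randomized arm. The plan reports medians, and the effect on those is not shown here.

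**The case against.** The strongest reply is that the plan is silent rather than wrong. A reader might infer that 24-month results are computed as though everyone were followed, and hence that harm and cost are both understated, more so in BIO. The documents do not support that. Section 8.2 names no denominator, and the only written safety rule, at 3 months, is exclusion. Step 4 shows that the direction of error depends on the rule chosen: down, none or up. Nor do the plan's expectations support a larger safety shortfall in BIO, where it expects no qualifying events at 3 months. INJ treatment is given at 0 and 6 weeks, so early events are plausible.

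A reader might also infer that cost is captured in proportion to follow-up time, about 70% and 82%. That assumes even accrual, but on the plan's assumptions treatment cost falls early. A session never attended is also a cost not incurred, rather than a missing one.

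Further, attrition is not identical to lost safety data. Section 5.3 counts outcomes missing for other reasons, Section 4.1.2 allows medical-record review and participant-initiated contact, and Section 9.4 provides for follow-up after treatment stops. The 15% rates are stated for non-responders only, and the analyses are descriptive.

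All of this stands, and it limits direction and size. It does not supply the missing rule or make a binomial interval suitable for censored follow-up. Excluding dropouts avoids bias in step 4 only because dropout is assumed independent of events, and it discards events already observed.

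**Conclusion.** The point holds as a missing rule joined to a method that cannot handle censoring. Expected loss by 24 months is about 42% (BIO) and 31% (INJ) by arm, or about 45%, 38% and 24-29% in the groups compared. These figures rest on extending non-responder attrition to everyone and, for the groups, on all non-responders adding a treatment. In the 10% illustration the reported risk ranges from 7.1% to 11.9% through the denominator alone. On the plan's own expectations the safety effect is nil in BIO, and in INJ small under the all-participant denominator. For cost, 73% (BIO) and 94% (INJ) of mean societal cost would be captured if cost after dropout were set to zero, which the plan does not say it will do. The matter should be settled before the data are examined. It does not touch the 3-month primary safety and cost comparisons.

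**What to change.** In Section 8.2:
- **Safety.** Replace the Wilson percentages at 6, 12, 18 and 24 months with Kaplan-Meier cumulative incidence of the first qualifying event, with 95% confidence intervals, censored at last adverse-event contact.
- **Groups.** For combination groups, start the clock at the added treatment. For therapy alone, censor participants who add a treatment at that point. Compare groups over equal follow-up time; combination curves will reach about 21 months at most (24 − 3).
- **Cost.** Keep the planned median. State who enters it, and that cost after last contact is missing rather than zero. Add a censoring-adjusted estimate as a sensitivity analysis, for example multiple imputation by assessment interval (0-3, 3-6, 6-12, 12-18 and 18-24 months).

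The change is to the wording of the analysis plan plus modest extra analysis. Adverse events and costs are already scheduled at 3, 6, 12, 18 and 24 months (Table 2). The price is wider intervals at late time points and reliance on independent censoring, including at the switch to an added treatment; the plan should state that assumption.

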### 1.1 Specific Aims

- A. Compare the effectiveness, safety, and cost of two treatments for moderate to severe FI in 194 male and female patients in a multi-center RCT; the interventions are biofeedback therapy (5 required weekly sessions with the option of an additional 6th visit, as needed) and perianal injection of the inert bulking agent dextranomer (INJ; Solesta). A ≥75% reduction in average weekly FI episodes compared to baseline will define a responder. The primary efficacy analysis will occur 3 months following the start of each treatment, with long-term follow-up through 2 years. Secondary outcomes will include a validated FI severity scale, a disease-specific quality of life scale, and measures of psychological distress.
  - Research objective 1 (primary). For the primary test of efficacy, the null hypothesis is that the proportion of responders in the two treatment groups will not be different. Secondary analyses will test for equivalence at other time points (e.g., 6, 12 and 24 months follow up) and will compare treatment groups on other secondary outcome measures.
  - Research objective 2 (primary). For the primary test of safety, the null hypothesis is that at 3 months follow up, the proportion of patients with adverse events (AEs) of pelvic pain of grade II or higher based on Common Terminology Criteria for AE (CTCAE) criteria, treatment site infection, or SAEs requiring hospitalization will not be different in the BIO or INJ groups. Secondary analyses will evaluate this outcome at 6, 12, 18, and 24 months follow up.
  - Research objective 3 (primary). At 3 months follow up, the estimated average cost for enhanced medical management non-responders will not be different for the two treatments. Secondary analyses will evaluate this outcome at 6, 12, 18, and 24 months.
- B. Compare efficacy in patients who complete all assigned treatment visits. Efficacy may be influenced by the number of BIO treatment sessions and the requirements to learn and practice new skills. Thus, in a secondary analysis, the primary efficacy outcome will be compared between treatment groups in the subset of participants who completed the treatment to which they were randomized.

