Tjandra compared the effects of SNS to "optimal medical management" in 120 patients with at least weekly solid or liquid FI. The control intervention included pelvic floor exercises taught by digital rectal examination and loperamide if needed. Controls were seen approximately once per month in the first 6 months. By ITT analysis, 68% of SNS treated patients achieved at least a 50% reduction in FI by six months, and 42% achieved continence. Controls showed no improvement at all, which raises concerns about the credibility of the control condition for the patients randomized to control.

Thin reported an underpowered RCT (described as a pilot study) which compared 19 patients treated with SNS to 17 treated with posterior tibial nerve stimulation (PTNS). No between-group statistical tests were reported but the trends favored SNS: 61% of SNS patients and 47% of PTNS patients met the responder criterion of a 50% reduction in FI episodes at 6 months. Leroi published a randomized cross-over study comparing simulator-on to stimulator-off periods which is often cited in support of SNS; however, the 27 subjects in this study were likely unmasked because they could probably feel when the stimulator was on.

Tan carried out a meta-analysis of available RCTs plus 32 reports on case series and concluded that SNS reduces incontinence episodes, improves ability to defer defecation, improves quality of life, and increases anal pressures. ClinicalTrials.gov identified one other ongoing cross-over study (NCT02163187) which is evaluating SNS in patients with FI following surgery for rectal cancer.

Wexner reported there were 13 treatment-related infections (AEs) including seven that required surgical intervention (serious adverse events, abbreviated SAE) in his series of 120 patients. In his meta-analysis of 34 publications, Tan estimated the complication rate as 15% with 3% requiring permanent explant (considered SAEs). Medicare reimbursement for SNS is approximately \$18,450.

With SNS, improvement in FI frequency is associated with relatively minor effects on anorectal function. One study observed that SNS but not sham stimulation increased the frequency of retrograde propagated sequences throughout the colon, which may be anticipated to delay colonic transit.

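### Section 8.2 names only median cost through 24 months, while research objective 3 is about average cost; arm medians would understate the cost of later SNS

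*Combined protocol and SAP*

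**What the plan says.** Section 1.1, research objective 3, sets the primary cost hypothesis: "At 3 months follow up, the estimated average cost for enhanced medical management non-responders will not be different for the two treatments". It then adds: "Secondary analyses will evaluate this outcome at 6, 12, 18, and 24 months".

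For the 3-month analysis, Section 8.1 is in line with this: "Mean and median costs per participant will be estimated for each of the two treatment groups", with t-tests or bootstrapping for the difference.

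For the longer term, the cost paragraph of Section 8.2 reads: "The median costs per participant from the perspectives of payers, patients, and society through 24 months will be estimated". The sentence goes on to cover each treatment group, "including the treatment combinations, using methods described for the primary cost of care endpoint". No formal testing is planned there, and p-values are informational.

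SNS is offered only after 3 months, to non-responders. Section 5.4 gives the expected uptake: "we could expect 40 patients to choose the SNS treatment, 32 to choose BIO, and 9 to choose INJ".

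**The concern.** The statistic named for 6 to 24 months is not the one in the objective. A payer's total spending is the mean cost times the number treated. The median cannot be scaled up in that way, nor can it serve as the cost in a cost per QALY.

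The gap matters most after 3 months. That is when the most expensive treatment in the study becomes available, to a minority of each arm and mainly to participants first assigned to INJ. If the long-term cost comparison rests on arm medians, most of that later cost will not appear in it, and the INJ minus BIO difference will look smaller than the difference in average cost that the objective asks about.

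**Working it through.** **Inputs**
- Randomized: 97 per arm. Expected 3-month completers: 78 BIO, 92 INJ (Section 5.4).
- Response at the 75% criterion: 78% BIO, 32% INJ (Table 1).
- Choice among non-responders: equal between the two options (Section 5.4).
- Treatment cost: BIO $796, INJ $10,363 (Table 5).
- SNS: $18,450 by Medicare reimbursement (Section 2.2.3), the basis Section 4.1.3 prescribes for payer cost. Table 1 gives $29,000 to $69,000, used here as a sensitivity range.

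**Reproducing the plan's figures**
- Non-responders: 78 × 0.22 = 17.2 (stated 17); 92 × 0.68 = 62.6 (stated 63).
- Choosing SNS: (17 + 63)/2 = 40. Choosing BIO: 63/2 = 31.5 (stated 32). Choosing INJ: 17/2 = 8.5 (stated 9).
- Table 5: 3 × 265.45 = $796; 2 × (281.03 + 4,900) = $10,362 (stated $10,363).

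**Share of each randomized arm adding SNS**
- INJ: 31.5/97 = 32.5%. BIO: 8.5/97 = 8.8%. Both are below half.
- INJ would reach half only if 48.5/63 = 77% of its non-responders chose SNS.

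**Mean cost added after 3 months, per randomized participant, SNS at $18,450**
- INJ: (31.5 × 18,450 + 31.5 × 796)/97 = $6,250.
- BIO: (8.5 × 18,450 + 8.5 × 10,363)/97 = $2,525.
- Net: 6,250 − 2,525 = $3,725.

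**Arm means**
- INJ: 10,363 + 6,250 = $16,613. BIO: 796 + 2,525 = $3,321. Difference: $13,292.

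**Arm medians**
- BIO: 80 of 97 stay at $796, so the median is $796.
- INJ, in order: 34 at $10,363, 31.5 at $11,159 (10,363 + 796) and 31.5 at $28,813 (10,363 + 18,450). The 49th value is $11,159.
- Difference: 11,159 − 796 = $10,363.

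**Response to the SNS price**

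| SNS price | INJ mean | BIO mean | Mean difference | Median difference |
|---|---|---|---|---|
| $18,450 | $16,613 | $3,321 | $13,292 | $10,363 |
| $29,000 | $20,039 | $4,245 | $15,794 | $10,363 |
| $69,000 | $33,029 | $7,750 | $25,278 | $10,363 |

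**Sensitivity of the $3,725**
- The SNS part is (31.5 − 8.5) × 18,450/97 = $4,375. Crossover to the other randomized treatment offsets 8.5 × 10,363/97 − 31.5 × 796/97 = 908 − 258 = $650.
- Section 2.2.3 says 10% to 30% fail to qualify for a permanent implant. If they cost nothing (an assumed lower bound, since the test itself has a cost), the net is 0.9 × 4,375 − 650 = $3,288 to 0.7 × 4,375 − 650 = $2,413.
- If only 25% of non-responders chose SNS and the rest the other treatment (an assumption), INJ adds 63 × (0.25 × 18,450 + 0.75 × 796)/97 = $3,384 and BIO adds 17 × (0.25 × 18,450 + 0.75 × 10,363)/97 = $2,171, a net of about $1,213.

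**The case against.** The best defence is the rest of the sentence in Section 8.2. It borrows the primary cost methods, which include means, and t-test p-values would compare means anyway. This reading is possible. But the sentence names its own statistic, and a general reference to methods does not clearly override it. A t-test p-value could also end up beside medians that it does not test. The text is at best ambiguous.

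A reader might infer that the medians ignore SNS altogether. The documents do not support that, for two reasons.
- Costs are also estimated by treatment combination. In the BIO-then-SNS and INJ-then-SNS groups everyone chose SNS, so those medians ($19,246 and $28,813 on the inputs above) show its cost. But these groups form by choice after randomization, the first is expected to hold only 8 or 9 people, and their medians cannot be combined into an average per randomized arm.
- Arm medians do move by rank. In the calculation above the INJ median goes from $10,363 to $11,159. If INJ costs varied normally (an assumption) with Table 5's SD of $4,032, adding $18,450 to 32.5% of the arm would raise the median by about $2,600, against 31.5 × 18,450/97 = $5,991 for the mean. The median understates the cost; it is not blind to it.

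A reader might also infer that mean costs through 24 months will never be computed. Research objective 9 and the cost-effectiveness analysis in Section 8.3 use average cost per QALY, so they will have to be. The medians do not contradict that analysis. They leave the cost paragraph without the quantity its own objective names.

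The 50% uptake may be too high. Section 2.3 withholds SNS from some participants, and survey respondents in Section 5.5 were less willing to try SNS than either other treatment.

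**Conclusion.** The mismatch stands. The objective concerns average cost through 24 months, and the paragraph that should deliver it names only the median. It is also not explicit that whole randomized arms will be reported: the parallel safety paragraph in Section 8.2 separates each therapy alone from the treatment combinations.

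On the plan's flow with SNS at $18,450, the arm difference is about $13,300 in means and $10,363 in medians. Crossover treatments account for about $3,700 of the mean difference. Counting SNS alone would overstate that part at about $4,375.

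These sizes assume two injections for every INJ participant, full SNS cost for everyone who chooses it, 50% uptake, dropouts carrying the cost of their assigned treatment, and no other medical costs. Lower SNS uptake or fewer implants shrink the gap. The higher Table 1 prices widen it.

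The consequence is limited. This is a secondary analysis without formal testing, and the 3-month primary cost analysis already includes means. The risk is a long-term cost summary that misrepresents average cost by arm, which is worth a small correction.

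**What to change.** In the cost paragraph of Section 8.2, change 'The median costs' to 'Mean (with bootstrap 95% CI) and median costs'. State that they are reported by randomized arm at 6, 12, 18 and 24 months, with treatment combinations reported descriptively.

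This is a wording change. The cost data are already scheduled at those times, and Section 8.1 already provides for means, medians and bootstrapping, so the 3-month code can be reused. The median is kept.
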